13.3 Reporting of adverse events

AEs reported by the subject or observed by the investigator must be recorded on the AE form of the eCRF and should be described in the following manner:

The *AE term* must be in precise English medical terminology (that is, not necessarily the exact words used by the subject). Whenever possible, a specific diagnosis should be stated (for example 'allergic contact dermatitis').

For cutaneous AEs the *location* must be part of the AE description and may be described as e.g., the face, scalp, back, chest, arm, leg, trunk, or limb. Additionally, the location should be described using the following terminology:

- Lesional/perilesional (≤ 2 cm from the border of lesion(s) treated with IMP).
- Distant (> 2 cm from the lesion border).

The *duration* of the AE must be reported by the start date and stop date of the event (it will also be recorded if the event is ongoing). In addition, it will be recorded if the AE started prior to start of IMP.

AEs must be classified in terms of severity, causality and outcome according to the definitions in [Appendix 2](#).

Action taken with IMP: any action taken with IMP as a consequence of the AE must be recorded (dose not changed, drug withdrawn, not applicable, unknown).

Other action taken: any other action taken as a result of the AE must be recorded (none, concomitant medication, concurrent procedure).

Withdrawn from trial due to this AE: it must be recorded whether the AE led to withdrawal from the trial.

13.4 Reporting of serious adverse events

The criteria that define an AE as serious (that is, an SAE) are defined in [Appendix 1](#). SAE criteria are also listed on the SAE form.

13.4.1 Investigator reporting responsibilities

Any SAE must be reported to LEO on the (paper) SAE form within 24 hours of first knowledge. This report should contain an assessment of available information on seriousness, severity, causal relationship to the IMP or trial procedure, the action taken, the outcome to date, and a narrative description of the course of the event.

The completed SAE form must be faxed or scanned and e-mailed to Global Pharmacovigilance at LEO using the e-mail address or fax number below:

Global Pharmacovigilance at LEO

E-mail address: [contact]

[contact]

If relevant, the investigator will enclose other information with the SAE form, such as anonymised reports of diagnostic procedures, hospital records, autopsy reports, etc.

Additionally, Global Pharmacovigilance at LEO may request further information in order to fully assess the SAE. The investigator must forward such information to LEO upon request by fax or e-mail (see contact details above).

The investigator must notify the local IRB(s)/IEC(s) of SAEs, as required by current applicable legislation for the concerned country.

SAEs occurring after the completion of the clinical trial should not be routinely sought or collected. However, such events should be reported to Global Pharmacovigilance at LEO (see contact details above) if the investigator becomes aware of them.

13.4.2 LEO reporting responsibilities

Global Pharmacovigilance at LEO is responsible for assessing whether or not an SAE is expected. The relevant reference safety information document for this clinical trial is:

For the IMP, the Investigator's Brochure, edition 1 and subsequent updates must be used.

Global Pharmacovigilance at LEO will notify the regulatory authorities and concerned investigators of SAEs according to the current applicable legislation for the concerned countries.

The IRB(s)/IEC(s) will be notified of SAEs according to the current applicable legislation for the concerned countries.

For all non-US countries, the following reporting requirements apply: all SAEs which are assessed as causally related to the IMP **by either the investigator or LEO** (ICH E2A Guideline), and which are unexpected (Suspected, Unexpected Serious Adverse Reactions [SUSARs]), are subject to expedited reporting to regulatory authorities and IEC(s)/IRB(s) according to the current applicable legislation in the concerned countries. Investigators will be notified of the evolving safety profile of the IMP on an ongoing basis.

For the US, the following reporting requirements apply: all SAEs which are assessed as causally related to the IMP **by LEO** (Guidance for Industry and Investigators - Safety Reporting Requirements for INDs and BA/BE Studies; Guidance for Clinical Investigators, Sponsors, and IRBs: Adverse Event Reporting to IRBs – Improving Human Subject Protection) and which are unexpected (Serious and Unexpected Suspected Adverse Reactions [IND safety report]) are subject to expedited reporting to regulatory authorities and IRB(s). Investigators will be notified of the evolving safety profile of the IMP on an ongoing basis.

13.5 Other events that require expedited reporting

13.5.1 Pregnancy

Any pregnancy occurring during the clinical trial must be reported to LEO within 24 hours of first knowledge using the (paper) Pregnancy Form (Part I). All pregnancies must be followed up until delivery or termination and final outcome must be reported on the (paper) Pregnancy Form (Part II) within 24 hours of first knowledge.

The completed Pregnancy Forms must be faxed or scanned and e-mailed to Global Pharmacovigilance at LEO. Contact details are given in Section [13.4.1](#).

Pregnant subjects must immediately discontinue IMP permanently (Sections [10.2.1](#) and [10.3](#)).

13.6 Reporting of other events

13.6.1 Adverse events of special interest

The event listed in [Panel 15](#) is considered an adverse event of special interest in this trial and will require that the investigator provides additional details to be recorded in the eCRF. An adverse event of special interest may be serious (requiring expedited reporting, Section [13.4](#)) or non-serious.

Panel 15: Adverse event of special interest

Adverse event of special interest	Additional information to be provided
Eczema herpeticum	
Skin findings:
 
• Lesion type.• Disseminated/localised.• Location.• Present in area with visible eczema/no visible eczema/present in areas with and without eczema.• Monomorphic/polymorphic. 
Confirmation of herpes simplex virus.

13.6.2 Overdose

An overdose is defined as a subject using more than double the recommended quantity of IMP specified in this protocol in Section 9.2. An overdose is either accidental or intentional.

The term ‘overdose’ including a specification of why it occurred (accidental or intentional) must be documented on the AE form of the eCRF. In addition, AEs originating from an overdose must be documented on a separate line. If the AE originating from the overdose qualifies as an SAE, expedited reporting is required (Section 13.4).

13.6.3 Medication error

Medication error refers to any unintentional error in the dispensing or administration of an IMP while in the control of the investigator or subject. Broadly, medication errors fall into 4 categories: wrong medication, wrong dose (including strength, form, concentration, amount), wrong route of administration, or wrong subject.

The medication error category must be documented on the AE form in the eCRF. In addition, AEs originating from a medication error must be documented on a separate line. If the AE originating from the medication error qualifies as an SAE, expedited reporting is required (Section 13.4).

13.6.4 Misuse

Misuse refers to situations where the IMP is intentionally and inappropriately used not in accordance with the protocol.

The term ‘misuse’ must be documented on the AE form in the eCRF. In addition, AEs originating from misuse must be documented on a separate line. If the AE originating from misuse qualifies as an SAE, expedited reporting is required (Section 13.4).

13.6.5 Abuse

Abuse relates to the sporadic or persistent, intentional excessive use of an IMP which is accompanied by harmful physical or psychological effects.

The term ‘abuse’ must be documented on the AE form in the eCRF. In addition, AEs originating from abuse must be documented on a separate line. If the AE originating from abuse qualifies as an SAE, expedited reporting is required (Section 13.4).

13.6.6 Aggravation of condition

Any clinically significant aggravation/exacerbation/worsening of any medical condition(s) (including the trial disease), compared to screening, must be reported as an (S)AE in accordance with Sections [13.3](#) and [13.4](#).

13.7 Follow-up for final outcome of adverse events

During the trial, the investigator should follow up for final outcome on all AEs (including SAEs). Once a subject leaves the clinical trial, the investigator should follow up on the outcome of all non-serious AEs classified as of possibly/probably relationship to the IMP for 14 days or until the final outcome is determined, whichever comes first. SAEs must be followed up until a final outcome has been established, that is, the follow-up may continue beyond the end of the clinical trial. For SAEs which have stabilised and cannot be expected to resolve during the trial or the safety follow-up periods, for example chronic or stabilised conditions, ‘not resolved’ is accepted as a final outcome and a statement that the SAE has stabilised or is chronic should be added to the narrative in the SAE form.

13.8 Handling of an urgent safety measure

An urgent safety measure is a measure taken to implement an action/protocol deviation under an emergency. This is defined as “*...the occurrence of any new event relating to the conduct of the trial or the development of the investigational medicinal product where that new event is likely to affect the safety of the subjects, the sponsor and the investigator shall take appropriate urgent safety measures to protect the subjects against any immediate hazard.*” [\(22\)](#).

If the investigator becomes aware of information that necessitates an immediate change in the clinical trial procedure or a temporary halt to the clinical trial in order to protect clinical trial subjects from any immediate hazard to their health and safety, the investigator can do so without prior approval from LEO, regulatory authorities, or IRBs/IECs.

The investigator must immediately inform LEO – by contacting the clinical project manager or medical expert – of this change in the clinical trial procedure or of the temporary halt providing full details of the information and the decision making process leading to the implementation of the urgent safety measure.

LEO must act immediately upon receipt of the urgent safety measure notification in accordance with internal procedures and local legislation.

14 Statistical methods

14.1 Sample size

A total of 250 subjects will be divided into 5 treatment groups and randomised 1:1:1:1:1 to one of each dose level of delgocitinib cream (1, 3, 8, or 20 mg/g) or delgocitinib cream vehicle.

The sample size is based on the following pairwise consideration, even though the primary objective of the trial is to establish the dose-response relationship. With a significance level of 5% when comparing 2 treatment groups and assuming treatment success rates (according to IGA) of 45% and 15%, respectively of the investigative treatment group (delgocitinib cream) and delgocitinib cream vehicle, then 50 subjects per treatment group will provide a power slightly above 90% for finding significantly different success rates between treatment groups.

14.2 Trial analysis sets

All screened subjects will be accounted for in the CTR.

All randomised subjects will be included in the full analysis set and will be analysed for efficacy parameters up to Week 16. Exclusions from the full analysis set can be considered in special cases as described in ICH E9, Section 5.2.1., Full Analysis Set. If it is decided to exclude a randomised subject from the full analysis set, a justification addressing ICH E9 will be given.

A per protocol analysis set will be defined by excluding subjects from the full analysis set who fulfil any of the following criteria:

- Did not receive treatment with the IMP.
- Did not provide IGA or HECSI data following start of treatment.
- Are known to have taken the wrong IMP throughout the treatment period of the trial.
- Did not fulfil the disease defining inclusion criteria (that is, inclusion criteria 3, 4, and 5).
- Did not apply IMP at least 80% of the time in the period from date of first application of IMP to date of last application of IMP.

A safety analysis set will be defined by excluding subjects from the full analysis set who receive no treatment with IMP.

Based on the above rules, the decisions regarding inclusion/exclusion of subjects and/or subject data from the trial analysis sets will be documented in the analysis set definition document before breaking the randomisation code.

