14.3.3 Exposure and treatment compliance

The duration of exposure to treatment in a specific visit interval will be calculated as the number of days from date of first application of IMP in that period to the date of last application of IMP in that period, both days included.

Exposure to treatment will be presented for the safety analysis set as days of exposure per treatment group.

Drug accountability data will be calculated by subtracting the weight of the used tubes from the mean normal weight of full tubes. Average weekly/bi-weekly and total usage will be presented per treatment group, respectively, both for time intervals between visits (1 or 2-week periods depending on the time between site visits) and total period.

Adherence to treatment regimen will be recorded in the eCRF. If any complications or deviations in administration are observed, these will be described as protocol deviations.

Adherence will be presented for the safety analysis set for each treatment group via the percentage of applications missed.

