14.3.9 Analysis of safety

The analysis of safety will be based on the safety analysis set.

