14.3.9.1 Adverse events

AEs will be coded during the course of the trial according to Medical Dictionary for Regulatory Activities (MedDRA). AEs will be presented by preferred terms and primary system organ class (SOC).

Treatment-emergent AEs will be summarised; however, all AEs recorded during the course of the trial will be included in subject data listings. An event will be considered treatment-emergent if started after the first use of IMP or if started before the first use of IMP and worsened in severity after first dose of IMP. The tabulations described in the following will only include the treatment-emergent events. In each of the tabulations, AEs are defined by MedDRA preferred terms within primary SOC.

An overall summary of the number of events and the number (percentage) of subjects with any treatment-emergent AEs, deaths, SAEs, premature discontinuations from the trial due to AEs, treatment-related AEs and severe AEs will be presented.

The number of AEs and number of subjects with each type of AEs will be tabulated by treatment group.

The severity for each type of AE will be tabulated by treatment group. Where there are several recordings of severity for a given type of AE, severity will be taken as the most severe recording for that AE.

The causal relationship to IMP for each type of AE will be tabulated by treatment group. Where there are several recordings of causal relationship to the IMP for a given type of AE, causal relationship will be taken as the most-related recording from the last report of that AE, since that is when the investigator will be in possession of most information and so best able to judge causal relationship.

Related AEs are defined as AEs for which the investigator has not described the causal relationship to IMP as 'not related'. The number of subjects with each type of related AE will be tabulated.

SAEs will be evaluated separately and a narrative for each will be given.

Adverse events of special interest will be tabulated by treatment group.

AEs leading to withdrawal from trial and AEs leading to permanent discontinuation of IMP will be tabulated by treatment group.

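### The safety set is derived from the full analysis set, so a treated subject excluded from the full analysis set would also drop out of the summary safety and exposure tables

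*Combined protocol and SAP*

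**What the plan says.** Section 14.2 starts from an inclusive rule: "All randomised subjects will be included in the full analysis set and will be analysed for efficacy parameters up to Week 16". It then opens an exception: "Exclusions from the full analysis set can be considered in special cases as described in ICH E9, Section 5.2.1., Full Analysis Set". The condition attached is a written one: "If it is decided to exclude a randomised subject from the full analysis set, a justification addressing ICH E9 will be given". The protocol does not list the special cases and does not confine them to subjects who never used IMP.

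The safety set is then built on what remains: "A safety analysis set will be defined by excluding subjects from the full analysis set who receive no treatment with IMP".

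Two later sections rely on that set. Section 14.3.9 says "The analysis of safety will be based on the safety analysis set", and its subsections cover adverse events, vital signs, laboratory evaluation and local tolerability. Section 14.3.3 says "Exposure to treatment will be presented for the safety analysis set as days of exposure per treatment group", and it presents adherence for the same set.

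Some outputs lie outside the set. Section 14.3.9.1 states that "all AEs recorded during the course of the trial will be included in subject data listings". Sections 14.3.1 and 14.3.2 present disposition and baseline characteristics for all randomised subjects. Section 14.2 also requires that decisions on set membership be documented before unblinding.

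**The concern.** The full analysis set exists to answer the efficacy question, and a decision to remove someone from it is judged on that ground. The safety set should answer a different question: what happened to everyone who was exposed. Because the second set is nested in the first, an efficacy-population decision also decides who is counted for harm.

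At stake are the denominators and event counts in the safety tables. Comparing safety with vehicle is a stated objective of the trial, the number of adverse events is the listed safety endpoint (section 6), and the results are meant to support dose selection for phase 3 (section 5.3). With small arms, one missing subject can be visible in the table for an uncommon event.

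**Working it through.** This is mainly a question of set logic. The plan gives no figure for the safety set that could be reproduced.

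**Inputs.** Section 14.1: 250 subjects, 5 groups, equal allocation, so 250 / 5 = 50 per arm, as the plan states. Section 14.2: the set definitions given above.

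**Step 1, the definitions as written.** Let R be all randomised subjects, E those excluded from the full analysis set as special cases, and T those who received IMP.

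- Full analysis set = R without E.
- Safety set = full analysis set without the untreated = (R without E) and T.
- All randomised and treated subjects = R and T.

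The difference between the last two is E and T, that is, treated subjects who were excluded from the full analysis set.

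**Step 2, when the difference is empty.** If E is empty, or holds only untreated subjects, the two sets are identical.

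**Step 3, whether the text keeps it empty.** It does not. Section 14.2 removes untreated subjects in separate steps, from the per protocol set and from the safety set. Untreated subjects are thus expected to be in the full analysis set by default, and the special cases are not simply another name for them. No sentence returns a treated, excluded subject to the safety set.

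**Step 4, size, as an illustration.** The documents do not say how many exclusions to expect, so the number k of treated subjects excluded from one arm is an assumption. With x subjects having an event in an arm of 50, and j of the k excluded subjects among them, the tabulated incidence changes from x/50 to (x − j)/(50 − k).

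| Assumed k | Safety denominator in the arm | Trial total |
|---|---|---|
| 1 | 50 − 1 = 49 | 250 − 1 = 249 |
| 2 | 50 − 2 = 48 | 250 − 2 = 248 |
| 3 | 50 − 3 = 47 | 250 − 3 = 247 |

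For k = 1:

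- Excluded subject had the arm's only case (x = 1, j = 1): 1/50 = 2.0% becomes 0/49 = 0%.
- Excluded subject had no event, with five cases in the arm (x = 5, j = 0): 5/50 = 10.0% becomes 5/49 = 10.2%.

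The 2-point change is the worst case for one subject. Without an event in the excluded subject, the shift is a small change of denominator.

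**The case against.** The strongest reply is that the situation may never arise. Exclusion from the full analysis set is exceptional, needs a justification and is settled before unblinding. This stands as to likelihood, and it limits selection by treatment arm. It does not put a lost subject back in the table, and a definition should still work when the plan's own exception is used.

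A second reply is that the events do not vanish. This also stands. All recorded adverse events are listed, disposition covers all randomised subjects, and expedited reporting of serious events (section 13.4) does not depend on analysis sets. The promise of a narrative for each serious event carries no set restriction of its own, although it sits under the general sentence on the safety set. Listings do not, however, correct denominators or incidence rates, nor the laboratory, vital sign, tolerability and exposure summaries.

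A reader might go further and infer that subjects with entry failures, or with no efficacy data after baseline, would be the ones removed, and that the loss would be informative because some of them stopped early through harm. The documents do not support this. In section 14.2, failing the disease-defining entry criteria and lacking IGA or HECSI data after treatment start are grounds for leaving the per protocol set. Such subjects stay in the full analysis set by default, and in the safety set if treated. Section 14.3.5 counts subjects who withdraw without Week 16 data as non-responders, so they are kept too. The protocol points to ICH E9 for the special cases without reproducing them, so no particular ground for exclusion can be assumed.

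**Conclusion.** The point holds as a conditional defect of wording. As written, a treated subject excluded from the full analysis set also leaves the summary safety tables and the exposure and adherence summaries, and nothing in the documents restores that subject.

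The size is modest: 1 of about 50 per excluded treated subject in an arm, plus that subject's events. It is zero if nobody, or only untreated subjects, are excluded. This assumes the planned 50 per arm, essentially all treated; the number of exclusions is unknown. Exclusion from the per protocol set alone has no effect on the safety set.

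The documents do not support reading this as a disappearance of events from the report, or as a biased loss of early stoppers. The primary objective, the efficacy analyses and the power statement are untouched.

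**What to change.** Replace the safety set sentence in section 14.2 with: *The safety analysis set comprises all randomised subjects who received at least one application of IMP, whether or not they are in the full analysis set.*

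The cost is one sentence. If no treated subject is excluded, the new set is identical to the current one; otherwise it restores the exposed subjects to the tables. No sample size, efficacy analysis or trial procedure changes. Section 14.3.12 already allows a change to the planned analysis to be described and justified in the statistical analysis plan, which is to be finalised before the randomisation code is broken. The analysis set definition document should use the same wording.
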